In PsA but also in chronic arthritis in general, integrating imaging in clinical practice is the challenge of the near future and for clinical feasibility it is essential to identify an US composite score that could explore all the domains of the disease, especially in the polymorphic PsA.

In 2012 *Gutierrez et al.* developed a Power Doppler composite score focused on joints, tendons, entheses, skin and nails and the final target was to define the overall disease activity.⁽¹³⁾ The German US7-joints score is another viable tool for examining patients with chronic arthritis in daily practice. Developed mainly for RA, it was also effective for monitoring therapy in peripheral PsA.⁽¹⁴⁾ More recently *Ficjan et al* developed two new US composite scores (PsASon-13 and PsASon-22), derived from a total ultrasound score (68 joints/14 entheses) in order to have a high sensitivity to detect PsA features and a good feasibility in clinical practice.⁽¹⁵⁾ However no simplified scores are fully validated in terms of content, construct and criterion so far. For this reason extensive US evaluations are needed to assess PsA in clinical practice and research.

AIM

The aim of this study is to identify clinical and US predictors of achieving MDA in PsA patients with active peripheral arthritis starting a new course of therapy.

Identifying prognostic factors of achieving remission or low disease activity will allow a better selection of patients with poorer outcome and a following improvement of the therapeutic strategies. Furthermore the possibility that US could be an added prognostic value makes this study a clear example of integration between the clinic and US. This study will respond to the need of tailoring treatment that would allow clinicians to practice a more effective and personalized medicine, optimizing the outcomes of patients with PsA as well as the treatments management.

STUDY OBJECTIVES

PRIMARY OBJECTIVE

In clinically diagnosed PsA with clinically active joint disease starting a new course of therapy, to evaluate the additional value of US-score (US-score PsA-SIR) over clinical examination in detecting patients achieving MDA at 6 months.

SECONDARY OBJECTIVES

In clinically diagnosed PsA with clinically active joint disease starting a new course of therapy:

- to evaluate the additional value of US over clinical examination in detecting patients:
 - achieving MDA at 12 months (including sustained)

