 1. Physician completes VAS Physician global assessment of disease activity (joint and skin) 0-100;
 2. Patients completes pain VAS (0-100), global VAS (0-100), HAQ, PsAID12
- US assessment:
 1. US-score PsA-SIR
- X-ray assessment of hands and feet:
 1. Posterior-anterior radiographic assessments of hands and feet (electronic format)

CLINICAL ASSESSMENT

The demographic variables describing the patients will be age, sex, ethnic group, family history, body weight, height and smoking. On enrolment in the study, a detailed medical history will be recorded mostly focusing on PsA (onset of symptoms, date of diagnosis), related treatment (current and previous medication, reason for withdrawal) and associated comorbidities (e.g. SpA spectrum comorbidities). To assess comorbidities, disease specific recommendations will be followed.⁽¹⁷⁾

To increase feasibility and reliability metabolic syndrome will be defined as follows: 1) BMI > 30 kg/m²; 2) a diagnosis of type 2 diabetes mellitus and 3) a diagnosis of hypertension.⁽¹⁸⁾

Each patient considered eligible for the study will be classified according to clinical subset(s) of PsA:

- 1- Monoarticular or asymmetric oligoarthritis with or without dactylitis.
- 2- Symmetric polyarthritis similar to rheumatoid arthritis.
- 3- Classic psoriatic arthritis confined to distal interphalangeal joints of hands and feet.
- 4- Spondylitis with or without peripheral joint involvement
- 5- Arthritis mutilans

CLINICAL EFFICACY

Clinical response and clinical remission will be based on the following variables:

- 1- Minimal Disease Activity (MDA)
- 2- Disease Activity for Psoriatic Arthritis (DAPSA)
- 3- ACR response score

The sonographer should be blinded to minimize bias associated with disease activity score evaluation. In addition, every effort should be made to ensure that the same member of staff performs the disease activity assessment on successive visits for a given patient.

The MDA calculation will be based on the evaluation of 7 variables:

- a) 68 tender joints count (≤ 1)
- b) 66 swollen joint count (≤ 1)
- c) BSA ≤ 3
- d) Patient pain VAS (≤ 15 mm);
- e) Patient global disease activity VAS (≤ 20 mm);
- f) HAQ (≤ 0.5);
- g) Leeds Enthesitis Index (LEI) tender enthesal points (≤ 1)

Patients will be classified as having MDA if they meet 5 out of these 7 criteria (value in brackets).

The DAPSA calculation is based on the evaluation of 5 variables:

- a) 68 tender joints count
- b) 66 swollen joint count

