US IMAGING						
US-score PsA-SIR		X		X	X	X
CR IMAGING						
X ray (hands-feet)		X			X	X
ADVERSE EVENTS			X	X	X	X

STATISTICAL ANALYSIS PLAN

VARIABLES: OUTCOME MEASURES

PRIMARY:

- MDA at 6 months

SECONDARY

- MDA at 12 months, sustained MDA at 6 AND 12 months
- DAPSA <3.3 at 6 months, 12 months, 6 AND 12 months
- Δ mSvH 0-12 and 0-24 months
- Δ HAQ 0-12 and 0-24 months
- Δ PSAID 0-12 and 0-24 months
- US-score PsA-SIR damage subscore at 0-6-12 months

US PREDICTORS

- US-score PsA-SIR
- US-score PsA-SIR inflammation subscore
- US-score PsA-SIR damage subscore

CLINICAL PREDICTORS

Based on the relevant literature clinical variables to be considered in the model include:

- Demographic and environmental factors:
 - Age
 - Gender
 - Smoking
 - BMI
- Clinical factors:
 - subset of PsA
 - time from symptoms onset to diagnosis
 - disease duration
 - disease activity (DAPSA and BASDAI)
 - HAQ score
 - tender joints / pain
 - comorbidities (FM, MetS)
- Serological factors:
 - Acute phase reactants
- Therapy factors:
 - Treatment (NSAIDs, steroids, DMARDs)

DESCRIPTIVE ANALYSES

Descriptive data will be provided for all outcomes according to data type; number of patients (N), mean, standard deviation (for interval data), median 25% and 75% quartiles (for ordinal data). Frequency (absolute and relative) distributions will be provided for categorical data. Two-sided p-values will be presented throughout.

PRIMARY ENDPOINT ANALYSIS

Prediction of 6 months MDA will use multivariate adjusted logistic models. A baseline model will include all the clinical variables. US predictors will be added as covariates to the clinical variables, assuming an additive model. The derived β coefficients were used to calculate prognostic indices, thereby creating weighted prediction models.

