Model performance will be evaluated by C-indices (area under the ROC curve, AUC), net reclassification indices (NRI), integrated discrimination improvement (IDI), and plotted ROC curves. NRI can be used to compare the clinical impact of different models (it is a comparison of the proportion of subjects with disease who have appropriately increased risk scores with the new model, and the proportion of subjects without disease who have appropriately decreased risk scores with the new model). IDI represents desired improvements in average sensitivity corrected for undesirable increases in 1-specificity, it therefore compared whether the new models improved sensitivity without affecting specificity.⁽³⁰⁾

Data management and analysis will be performed using RedCap, R, Stata.

SECONDARY ENDPOINT ANALYSES

- to evaluate the additional value of US over clinical examination in detecting patients:
 - achieving MDA at 12 months
 - achieving sustained DAPSA remission at 6 and 12-months
 - achieving DAPSA remission at 6 and 12 months
 - achieving ACR Remission remission at 6 and 12 months
 - with X-ray structural progression (mSVH score) at 12 and 24 months
 - with US structural progression (US-damage score) at 12 and 24 months
 - with functional worsening (Δ HAQ>0.23) at 12 and 24 months
 - with impairment of HRQoL at 12 and 24 months

The same approach followed for the primary endpoint will be followed to evaluate

EXPLORATORY ANALYSES

- to evaluate the relationship between time-integrated US-detected inflammation and US-detected erosions at 12 and 24 months
- to evaluate the comparative effectiveness of different treatment strategies on MDA, DAPSA remission, Δ HAQ>0.23, X-ray progression (mSvHS), US-inflammation score, US-damage score.
- to evaluate the comparative effectiveness of different treatment strategies on MDA, DAPSA remission, Δ HAQ>0.23, , X-ray progression (mSvHS), US-inflammation score, US-damage score.

SAMPLE SIZE

The sample size calculation was done with the objective of minimizing the number of false positives (i.e the number of false non-responsive to treatment) in order to minimize the risk of over-treating patients who actually have a good response to therapy. Therefore, sample size was calculated to minimize this risk by 40% (null hypothesis H0) to 20% (alternative hypothesis H1), maintaining stable at 70% (both for the H0 for both the H1), the percentage of true positives (true unresponsive to therapy).

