The simulations were carried out using the procedure `rocsz` Stata (by M. Pepe)³⁰, which allows to determine the power to detect an improvement in the ROC curve. The procedure requires the specification of the percentage of false positive and true positive both for the null hypothesis is for the alternative hypothesis and the percentage of positive / diseased.

Using the command `rocsz 0.7 0.2, na (150) ndb (100) tnull (0.7) fnull (0.4)` of Stata, 250 patients are sufficient to evaluate the performance of a model (and its ROC curve) with 90% power and 5% alpha. Specifically, we have assumed a 70% and a 20% of subjects true positives and false positives, respectively, according to the alternative hypothesis, a 70% and a 40% of subjects true positives and false positives, respectively, according to the null hypothesis, and a percentage of diseased of 60% (150 of 250 subjects).

Under the assumption of maximum attrition of 20%, the sample size will be increased to 300 patients. The same sample size is sufficient to precisely estimate a logistic model of achievement of a MDA (probability of 0.4 at 6 months) with 10 predictors (rule of thumbs).⁽³¹⁾

Based on the pre-study activities, 35-40 centres will be involved, 15 tertiary and 20-25 secondary rheumatology centres. Assuming 4 eligible patients/months for tertiary and 1/month in secondary centres, a 40% of enrolment rate, about 30 patients/months are expected.

ETHICS

This study will be conducted in accordance with all applicable laws and regulations including, but not limited to, the International Conference on Harmonisation (ICH) Guideline for Good Clinical Practice (GCP), EU guidelines and the ethical principles that have their origins in the Declaration of Helsinki. The institutional review board (IRB)/independent ethics committee (IEC) must review and approve the protocol and informed consent form before any subjects are enrolled. Before any protocol-required procedures are performed, the subject must sign and date the IRB/IEC-approved informed consent form.

Clinical data (including AEs and concomitant medications) will be entered into a validated data capture system provided by the Italian Society for Rheumatology. The data system will include password protection and internal quality checks, such as automatic range checks, to identify data that appear inconsistent, incomplete, or inaccurate.

PUBLICATION RULES

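### No optimism correction is named for the clinical and clinical-plus-ultrasound models: both AUCs will on average be overstated, and the bias in the AUC gain changes sign with its true size

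*Combined protocol and SAP*

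**What the plan says.** The Primary Objective is "to evaluate the additional value of US-score (US-score PsA-SIR) over clinical examination in detecting patients achieving MDA at 6 months". Under Primary Endpoint Analysis, "A baseline model will include all the clinical variables", the US predictors are then added, and "The derived β coefficients were used to calculate prognostic indices, thereby creating weighted prediction models". The next paragraph says "Model performance will be evaluated by C-indices (area under the ROC curve, AUC), net reclassification indices (NRI), integrated discrimination improvement (IDI"), together with ROC plots. Secondary Endpoint Analyses carries the same approach to the other outcomes.

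No section mentions a hold-out sample, an external cohort, cross-validation, the bootstrap, shrinkage or any other correction for optimism. The only guard against overfitting is in Sample Size, which says the sample suffices for "a logistic model of achievement of a MDA (probability of 0.4 at 6 months) with 10 predictors (rule of thumbs").

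The Clinical Predictors list is longer than 10. It includes PsA subset, and Clinical Assessment gives five of these: "Each patient considered eligible for the study will be classified according to clinical subset(s) of PsA". Three US scores are listed as predictors. Ultrasonographic Assessment makes the total (0-632) the sum of the inflammatory (0-470) and damage (0-162) subscores.

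**The concern.** A model scored on the patients who determined its coefficients looks better than it will in new patients, and more so with more coefficients per event. The study aims to say whether US improves prediction enough to help select patients and guide strategy, so both the level of each AUC and the difference between them matter. It is natural to hope that the optimism cancels in the difference. It does not: the two models carry different amounts of it, and which carries more depends on how useful US is. A reader of the final report could not tell from the apparent figures which way the gain is off.

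**Working it through.** **The plan's own figure.** Sample Size sets TPR 0.7 and FPR 0.4 under H0, and "a 70% and a 20% of subjects true positives and false positives, respectively, according to the alternative hypothesis", with 150 diseased and 100 not. The Stata command was not run; a normal approximation for one ROC point, with equal-variance binormal curves, gives:
- d = z(0.7) - z(0.4) = 0.778 under H0 and z(0.7) - z(0.2) = 1.366 under H1.
- ROC(0.4) = 0.700 under H0 and 0.867 under H1, with slopes 0.900 and 0.556 at that point.
- Variance = R(1-R)/150 + slope² × 0.4 × 0.6/100, so SE = 0.0578 (H0) and 0.0389 (H1).
- Two-sided power at 5% = Φ((0.167 - 1.96 × 0.0578)/0.0389) = 0.917.

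The claim of 250 patients for 90% power therefore stands and is not at issue.

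**Inputs for the check.**
- Evaluable patients: 300 less 20% = 240. MDA events: 240 × 0.4 = 96.
- Clinical parameters: 10 (Sample Size), or about 20. The second is one reading of the list: age, gender, smoking and BMI 4; five subsets 4; time to diagnosis and duration 2; DAPSA and BASDAI 2; HAQ 1; tender joints and pain 2; FM and MetS 2; acute phase reactants 1-2; treatment 2-3. The total is 20-22. The coding is not stated.
- Events per parameter: 96/10 = 9.6; 96/20 = 4.8.
- True clinical AUC (assumption): Φ(0.778/√2) = 0.709, from the H0 point. The H1 point gives Φ(1.366/√2) = 0.833. Reading these as the models without and with US gives a gain of 0.124.

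**Simulation.** Both logistic models are fitted to 240 simulated patients and scored on the same patients (apparent) and on 10,000 new ones. There are 300 trials per cell and one US score, correlated 0.4 with the clinical index. The corrected column uses 60 bootstrap resamples with full refits.

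Clinical model AUC, useless US score:

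| Clinical parameters | Apparent | New patients | Corrected |
|---|---|---|---|
| 10 | 0.737 | 0.684 | 0.691 |
| 20 | 0.761 | 0.663 | 0.679 |

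The overstatement is 0.737 - 0.684 = 0.053 and 0.761 - 0.663 = 0.098. At the H1 point the combined model reads 0.850 against 0.817 (10 parameters) and 0.867 against 0.800 (20).

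AUC gain from one US term:

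| Clinical parameters | True gain | Apparent | New patients | Apparent minus new | Corrected |
|---|---|---|---|---|---|
| 10 | 0 | 0.0024 | -0.0022 | +0.0046 | -0.0018 |
| 10 | 0.02 | 0.0175 | 0.0196 | -0.0021 | 0.0168 |
| 10 | 0.05 | 0.0450 | 0.0529 | -0.0079 | 0.0498 |
| 10 | 0.124 | 0.1124 | 0.1330 | -0.0206 | 0.1283 |
| 20 | 0 | 0.0025 | -0.0016 | +0.0041 | -0.0006 |
| 20 | 0.02 | 0.0173 | 0.0199 | -0.0026 | 0.0187 |
| 20 | 0.05 | 0.0407 | 0.0538 | -0.0131 | 0.0492 |
| 20 | 0.124 | 0.1008 | 0.1365 | -0.0357 | 0.1260 |

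**Two US terms.** The three listed scores carry two independent terms, because 470 + 162 = 632. With independent predictors and n = 240, apparent minus new-patient gain is:
- 10 clinical terms: +0.008 at true gain 0.01, +0.005 at 0.02, +0.003 at 0.03.
- 20 clinical terms: +0.005 at 0.01, +0.001 at 0.02, -0.006 at 0.04, -0.014 at 0.07, -0.031 at 0.124.

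The last value shows why the sign turns. Clinical optimism is 0.763 - 0.663 = 0.100 and combined optimism is 0.867 - 0.798 = 0.069; the difference is -0.031.

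**NRI and IDI, useless US.** With one term, category-free NRI is 0.09 apparent against 0.01 in new patients, and IDI is 0.003-0.004 against 0.000. With 20 clinical and two US terms (n = 250), they are 0.15 against 0.02 and 0.0075 against 0.000.

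**The case against.** The strongest reply is that the primary question concerns the difference, where the harm is small. That largely stands for a useless score: the apparent AUC gain averages about +0.002 with one US term and reaches 0.01 in only 5-7% of trials. A reader might infer that the plan manufactures a benefit for US on AUC; these figures do not support that.

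A reader might equally infer that the gain is always understated when US is useful. That fails too: with 10 clinical and two US terms it is still overstated at a true gain of 0.03.

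Nor does the plan state an AUC target. Sample Size sets one ROC point; reading its two hypotheses as the models without and with US, and converting them to AUCs, are assumptions. The shortfall also depends on the benchmark. Against the population gain of 0.124 it is 0.124 - 0.112 = 0.012 or 0.124 - 0.101 = 0.023 with one US term, less than against new-patient performance, where overfitting also weakens the clinical comparator.

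The count of about 20 parameters is a reading, since no coding is given and a patient may belong to more than one subset. The problem is present at 10 as well.

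Finally, the plan does not say outright that apparent performance will be reported. That is inferred from its naming no other data or method. None of this removes the overstatement of each AUC.

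**Conclusion.** The concern holds in limited form. Followed as written, the plan would on average, though not in every sample, report AUCs that are too high. For the clinical model the excess is about 0.05 with 10 parameters and 0.10 with about 20. For the combined model at the H1 point it is 0.850 - 0.817 = 0.033 and 0.867 - 0.800 = 0.067.

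The bias in the AUC gain is smaller. It runs from about +0.004 to +0.010 if US adds nothing, stays positive or near zero for small gains, and turns negative for large ones. The reversal lies at a true gain of roughly 0.01 to 0.05, depending on the number of clinical and US terms. Under the binormal reading of Sample Size, the apparent gain is about 0.10-0.11 against 0.13-0.14 in new patients.

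The sizes rest on 240 evaluable patients, 40% MDA, normal predictors and a clinical AUC of 0.709. With an assumed clinical AUC of 0.80 the pattern was the same (20 clinical and two US terms, n = 250: +0.007 at no gain, -0.012 at a gain of 0.07). This is an inexpensive improvement to the analysis. It does not show that the design or the sample size is unsound.

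**What to change.** In the SAP:
- Report both AUCs, the change in AUC and IDI as apparent and bootstrap optimism-corrected values with confidence intervals, refitting both models in full in each resample. Apply the same to the secondary endpoints.
- Report NRI descriptively and state its form. Its corrected value with a useless score is still 0.03 against 0.01. Although "Two-sided p-values will be presented throughout", a two-sided 5% z-test on NRI (not named in the plan) would reject in 7.5% / 8.2% of null trials with 10 / 20 parameters.
- Do not enter all three US scores in one model. Use the total US-score PsA-SIR, as in the Primary Objective, for the primary comparison and the subscores as secondary.

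The cost is SAP wording and a loop in R or Stata, both already planned; no new data are needed. The reported AUCs fall: the clinical model goes from 0.74 to 0.69 with 10 parameters and from 0.76 to 0.68 with 20. The correction is incomplete. With 20 parameters the clinical AUC remains about 0.02 high (0.679 against 0.663) and the gain at the H1 reading about 0.01 low (0.126 against 0.137). At a true gain of 0.02 with 10 parameters it does not help (0.0168 corrected, 0.0175 apparent, 0.0196 in new patients).

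Whether to name a single primary test of the US gain, by likelihood ratio or otherwise, is a separate decision for the sponsor and not part of this change.

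### The SAP takes the IDI to show better sensitivity with specificity preserved, but for the planned nested logistic models scored on their own data the specificity half is not an independent check

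*Combined protocol and SAP*

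**What the plan says.** In the SAP, Primary endpoint analysis, the outcome model is set out in three steps: "Prediction of 6 months MDA will use multivariate adjusted logistic models"; "A baseline model will include all the clinical variables"; and "US predictors will be added as covariates to the clinical variables, assuming an additive model". The clinical model is therefore nested in the clinical-plus-ultrasound model. On performance: "Model performance will be evaluated by C-indices (area under the ROC curve, AUC), net reclassification indices (NRI), integrated discrimination improvement (IDI), and plotted ROC curves". The IDI is then described: "IDI represents desired improvements in average sensitivity corrected for undesirable increases in 1-specificity". From that description the SAP draws an inference: "it therefore compared whether the new models improved sensitivity without affecting specificity".

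The Sample size section gives the error that the study is built around: "The sample size calculation was done with the objective of minimizing the number of false positives". A positive there is a patient who does not respond, and a false positive is a responder classed as non-responsive. The false-positive rate is to fall from 40% to 20% with true positives held at 70%, in 150 positives and 100 negatives.

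The SAP names no hold-out sample, cross-validation or bootstrap. It gives no risk cut-off and does not say that the two components of the IDI will be reported separately. It also does not say which class is positive for the IDI and NRI: the model predicts MDA, while the sample size treats non-response as the positive result.

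**The concern.** The description of the IDI as average sensitivity gain net of average loss of specificity is standard. The last clause goes further. It presents the IDI as a comparison that can tell whether sensitivity rose with specificity left intact. For that to be a check, the data must be able to return the other answer, with sensitivity up and specificity down. With nested logistic models scored on the patients they were fitted to, that answer is algebraically impossible.

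Specificity matters here because, with non-response as the positive class, a loss of specificity is the over-treatment risk that the Sample size section sets out to reduce. A reader who takes a positive IDI as evidence that specificity was preserved would be relying on something that follows from the fitting method. The reader would also be relying on an average over all cut-offs, not on the operating point that sized the study.

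**Working it through.** **Inputs from the SAP.** Nested logistic models for 6-month MDA (Primary endpoint analysis). 250 evaluable patients, 150 positive (non-responsive) and 100 negative (responsive); true positives 70% under both hypotheses; false positives 40% under the null and 20% under the alternative (Sample size).

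**Assumptions the SAP does not state.** Maximum likelihood with an intercept, the same complete cases in both models, and evaluation on the fitting data.

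**1. The plan's own figure.** The SAP gives no IDI value to reproduce. The figure that fixes the operating point is 250 patients. The two-proportion formula for 40% against 20%, 90% power, one-sided 5% and a continuity correction gives 98 negatives, so 98/0.4 = 245 in total, against 100 and 250 in the plan. Power at 100 negatives is 90.6%. The match is by formula only, since the code of the Stata command was not available. It agrees with the text: the study was sized on the false-positive rate at one ROC point.

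**2. The identity.** Averaged over cut-offs from 0 to 1, sensitivity equals the mean predicted risk in positives (IS), and 1 − specificity equals the mean predicted risk in negatives (IP). The intercept's score equation makes the fitted probabilities sum to the number of positives in each model:

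n1·IS + n0·IP = n1.

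Subtracting the clinical model from the ultrasound model gives

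n1·ΔIS + n0·ΔIP = 0, so ΔIP = −(n1/n0)·ΔIS and IDI = ΔIS − ΔIP = (1 + n1/n0)·ΔIS.

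**3. With the plan's numbers.**
- Non-response positive (150/100): ΔIP = −1.5·ΔIS and IDI = 2.5·ΔIS. For example, ΔIS = 0.02 forces ΔIP = −0.03 and IDI = 0.05 (check: 150 × 0.02 − 100 × 0.03 = 0).
- MDA as the event (100/150): ΔIP = −(2/3)·ΔIS and IDI = 1.67·ΔIS.

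Under either coding, one component determines the other.

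**4. Numerical check.** Eight scenarios of 1,000 simulated trials were run (250 patients, about 60% positive, 1 to 18 clinical and 1 to 2 ultrasound terms; independent normal covariates, an assumption). The identity held to within 1e-13. Average sensitivity rose while average specificity fell in 0 of 8,000. The IDI was zero or negative in 1.0% to 8.3% of trials when ultrasound was noise. When the noise-ultrasound models were scored on new patients the identity broke: sensitivity rose with specificity falling in 38% to 45%, and the IDI was zero or negative in 49% to 55%.

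**5. What the IDI says about the design point.** Non-response positive, 13 clinical terms plus one ultrasound term, 3,000 trials per effect:
- Useless ultrasound score: IDI above 0 in 94%. Among these, the false-positive rate at 70% true positives was higher with ultrasound in 32.5% and unchanged in 24%.
- Effects of 0.2, 0.3 and 0.4 log-odds per SD, IDI significant (z > 1.96): higher in 16.8%, 15.5% and 14.0%. At 0.6 it was 7.6%.

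**6. How much of step 5 is noise.** With 100 responders, one patient moves the false-positive rate by one point. In a further 1,500 trials per effect, the median worsening was about 2 points, and only 1% to 3% of trials with a positive IDI worsened by more than 5. The fitted models were then applied to 20,000 new patients. Among trials with a significant IDI, the ultrasound model was truly worse in 0.5% at effect 0.3, in 0% at 0.4, and in 17% at 0.2 (median 0.4 points). With a useless score, only 4% of trials reached z > 1.96.

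**The case against.** The strongest defence is that the clause only explains an index. No success criterion or treatment decision depends on it, and the SAP itself never ties the IDI to over-treatment. On averages over cut-offs, and in the fitting data, the statement is redundant and not false: when average sensitivity rises, average specificity does rise too. The same paragraph plans ROC curves, on which the false-positive rate at 70% true positives can be read, and an NRI described separately for those with and without disease. Either could show a specificity loss. The identity also rests on conditions that the SAP leaves unstated. It would fail with different complete cases in the two models, with optimism correction or new data, and possibly if the prognostic indices used simplified weights.

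All of this stands, and it rules out three stronger readings that a reader might infer:
- **That the IDI as a whole cannot fail.** Only the specificity half is tied to the sensitivity half; the IDI can be zero or negative.
- **That the 14% to 17% of simulated trials with a significant IDI and a higher false-positive rate show real harm.** Step 6 shows that they are mostly sampling noise at a single ROC point.
- **That the whole plan hides over-treatment.** The ROC curves and NRI are there, and the clause is one sentence.

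The defence does not rescue the clause itself. The SAP words it as something the IDI finds out, names no validation under which it could be found out, and plans no formal comparison at the point that sized the study.

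**Conclusion.** The concern holds, limited to one interpretive clause; it should be changed, but it does not undermine the primary analysis. Under nested maximum-likelihood logistic models with an intercept, fitted and scored on the same patients, the change in average (1 − specificity) is exactly −1.5 times the change in average sensitivity in the Sample size coding (−2/3 with MDA as the event), so it carries no separate information. This is algebra and does not depend on the simulation settings. It does depend on evaluation in the fitting data, which is the default reading because no validation is named, and it does not carry over to new patients.

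Separately, an average over cut-offs does not address the target of 40% falling to 20% at 70% true positives, whatever the data used for evaluation. The IDI remains a legitimate summary of discrimination; the fault is in the conclusion attached to it.

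**What to change.** In Primary endpoint analysis, delete the clause that begins after the definition of the IDI (from the words it therefore onward) and state that the IDI is reported as the difference in discrimination slopes. Define non-response as the positive class throughout, to match the Sample size section. Base any statement about specificity or over-treatment on the difference between the two models' false-positive rates at 70% true positives, with a bootstrap confidence interval that refits both models in each resample.

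The cost is one sentence and a few lines of code; no new data are needed. The interval at a single ROC point will be wide. As a rough guide, with 100 responders and rates of 40% and 20% treated as independent, the standard error is √(0.4×0.6/100 + 0.2×0.8/100) = 0.063, or about ±12 points at 95%. Correlation between the models would narrow this, and estimating the cut-offs would widen it. That width is a true picture of what the study can say about its own target.
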